14.2.5.3 Listing Conventions

- Listings will be sorted for presentation in order of treatment groups as above, patient number, visit/collection day, and visit/collection time.
- Missing data should be represented on patient listings as either a hyphen (“-”) with a corresponding footnote (“- = unknown or not evaluated”), or as “N/A”, with the footnote “N/A = not applicable”, whichever is appropriate.
- Dates should be printed in SAS® DATE9.format (“ddMMMyyyy”: 01JUL2000). Missing portions of dates should be represented on patient listings as dashes (--JUL2000). Dates that are missing because they are not applicable for the patient are output as “N/A”, unless otherwise specified.
- All observed time values must be presented using a 24-hour clock HH:MM or HH:MM:SS format (e.g., 11:26:45, or 11:26). Time will only be reported if it was measured as part of the study.
- Units will be included where available

14.2.5.4 Figure Conventions

- Unless otherwise specified, for all figures, study visits will be displayed on the X-axis and endpoint (e.g., treatment mean change from Baseline) values will be displayed on the Y-axis.

14.2.6 Footnotes

- A solid line spanning the margins will separate the body of the data display from the footnotes.
- All footnotes will be left justified with single-line spacing immediately below the solid line underneath the data display.
- Footnotes should always begin with “Note:” if an informational footnote, or a, b, c, etc. if a reference footnote. Each new footnote should start on a new line where possible.
- Footnotes will be present on the page where they are first referenced and thereafter on each page of the table, unless the footnote is specific only to certain pages. Patient specific footnotes should be avoided.

Lexicon Pharmaceuticals, Inc.
[name]
[name]

1003157

Lexicon Pharmaceuticals, Inc.

LX1606.302

Final V1.0

Statistical Analysis Plan

- Footnotes will be used sparingly and must add value to the table, figure, or data listing. If more than 6 lines of footnotes are planned, then a cover page may be used to display footnotes, and only those essential to comprehension of the data will be repeated on each page.
- The last line of the footnote section will be a standard source line that indicates the name of the program used to produce the data display, date the program was run, and the listing source (i.e., 'Program : myprogram.sas Listing source: 16.x.y.z').

15 QUALITY CONTROL

- SAS programs are developed to produce clinical trial output such as analysis data sets, summary tables, data listings, figures or statistical analyses. INC Research Standard Operating Procedure (SOP) 03.010.01 and 03.013.01 provide an overview of the development of such SAS programs.
- INC Research SOP 03.009.01 describes the quality control procedures that are performed for all SAS programs and output. Quality control is defined here as the operational techniques and activities undertaken to verify that the SAS programs produce the proper clinical trial output by checking for their logic, efficiency and commenting and by review of the produced output.

16 APPENDICES

Attachment 1: Table shells

Attachment 2: Listing shells

Attachment 3: Figure shells

Note to File

Subject: Addendum to Statistical Analysis Plan for Studies LX1606.301, 302, 303, and for the LX1606 Integrated Safety Summary (ISS)

RE: Calculation of Extent of Exposure for Open Label Phases of Studies LX1606.301 and LX1606.303, and Study LX1606.302, and in the LX1606 ISS

Date: November 3, 2015

CC: Lexicon- [REDACTED]
[REDACTED] INC- [REDACTED] Ipsen- [REDACTED]
[REDACTED] InStat Services: [REDACTED]

Background:

This note to file is intended to document the methodology to be used in estimating duration of exposure to LX1606 in the above studies and in the ISS for the interim summaries of data which are being provided for inclusion in regulatory submissions.

Study 302 and the Extension Periods of Studies 301 and 303 The referenced studies all provide open label treatment of 500 mg tid for all patients In these studies, the electronic Case Report Form (eCRF) design includes a single page (Study Drug Accountability Extension Period; SDAEP) which records information about study drug administration during the open-label period, including first dose date, last dose date, and compliance calculation. The SDAEP eCRF is intended to be completed when the patient completes or terminates early from the study. Because many of the patients in the open-label studies are currently continuing treatment, and will not have completed SDAEP forms, it is not possible to accurately estimate study drug exposure based on these pages for such patients.

Plan:

The following approach has been agreed:

- Where the SDAEP eCRF includes both the first dose and last dose dates, the patient's duration of open label treatment exposure will be calculated using these dates. If the page also includes study drug compliance information, these patients will also be included in the reporting of study drug compliance.
- Any patient without a last dose date will have their duration of exposure estimated by using the date of the last recorded visit in the eCRF (scheduled or unscheduled), up to and including the week 48 visit (ie, excluding Follow Up visits). The time on study drug will be estimated for these patients, but no estimation will be performed that includes study drug compliance, dose, or amount of drug received during the study.

- Where the SDAEP eCRF includes both the first dose and last dose dates, the patient's duration of open label treatment exposure will be calculated using these dates. If the page also includes study drug compliance information, these patients will also be included in the reporting of study drug compliance.
- Any patient without a last dose date will have their duration of exposure estimated by using the date of the last recorded visit in the eCRF (scheduled or unscheduled), up to and including the week 48 visit (ie, excluding Follow Up visits). The time on study drug will be estimated for these patients, but no estimation will be performed that includes study drug compliance, dose, or amount of drug received during the study.
- A review has been completed of all adverse events for all patients in the open-label extension periods to ascertain if any patients may have been identified on the AE eCRF as having discontinued the study, discontinued study drug, or interrupted study drug due to an adverse event, but do not have a last dose date on the SDAEP eCRF. Within the data extracted for these studies at this time, no such AEs exist.

Signed: [redacted]
[redacted] MD
[redacted] Clinical Operations

NOTE TO FILE

To: LX1606-1.302-CS Trial Master File (TMF)

From: [REDACTED] of Biostatistics and Data Management
[REDACTED] of Biostatistics

Re: Study LX1606-1.302-CS: Handling of the Week 84/End of Study (EOS) Efficacy Data in the Statistical Analysis for Patients who Discontinued from the Study Prior to Week 84

Date: November 23, 2015

-
- I. **Incident/Finding(s):** According to Section 7.5 of the Final Statistical Analysis Plan (dated 24Nov2014), efficacy data are to be summarized by study week based on the study's schedule of events (in Table 1 of the SAP; also in Appendix A of the protocol). However, the efficacy data recorded at Week 84/EOS include not only efficacy data assessed at the Week 84 visit for patients who completed the study, but also efficacy data assessed at the last visit (ie, EOS visit) for patients discontinued from the study prior to Week 84. This Note-to-File (NTF) describes how the EOS visit for the latter patients will be mapped, for purposes of tabular summaries and statistical analyses, to the appropriate analysis visit based on the EOS' actual study day (where Study Day 1 = day of first dose of study drug in this study).
- II. **Analysis Visits for EORTC QLQ-C30 and GI.NET21:** For patients who discontinued from the study and had EORTC data recorded at the Week 84/EOS visit, these data will be assigned to analysis visits as follows:

Analysis Visit	Target Study Day	Actual Study Day of the EOS Visit
Week 24	Day 168	Day 84 to 251
Week 48	Day 336	Day 252 to 419
Week 72	Day 504	Day 420 to 545
Week 84	Day 588	Day 546 to 588

- III. **Analysis Visits for Subjective Global Assessment (SGA) (11-point Numeric Rating Scale and Yes/No response to adequate relief question) and Plasma 5-HIAA:** For patients who discontinued from the study and had SGA data recorded at the Week 84/EOS visit, these data will be assigned to analysis visits as follows:

Analysis Visit	Target Study Day	Actual Study Day of the EOS Visit
Week 12	Day 84	Day 42 to 125
Week 24	Day 168	Day 126 to 209
Week 36	Day 252	Day 210 to 293
Week 48	Day 336	Day 294 to 377
Week 60	Day 420	Day 378 to 461

Analysis Visit	Target Study Day	Actual Study Day of the EOS Visit
Week 72	Day 504	Day 462 to 545
Week 84	Day 588	Day 546 to 588

- IV. If after applying II or III above, the Week 84/EOS visit with the efficacy data gets assigned to a visit that already contains data for the same efficacy parameter group (ie, EORTC or SGA or plasma u5-HIAA) for the patient, the rules described in Section 7.5 of the SAP for selecting among multiple records within the same analysis visit will be applied.
- V. **Action(s) Taken:** The Week 84/EOS efficacy data for patients who discontinued from the study prior to Week 84 will be assigned to appropriate analysis visits as specified in II and III above. The decision was made by Lexicon Biostatistics after review of the Draft 1 tables/listings based on the 16Oct2015 interim database extraction. It should be noted that this study is open-label, and there is no randomization to treatment. Patients are to continue on open-label telotristat etiprate at the dose level they are on at the end of their parent study.

[REDACTED]
[REDACTED] MS ERS/ [REDACTED] of Biostatistics

[REDACTED]
Date

[REDACTED]
[REDACTED] MS, [REDACTED] of Biostatistics

[REDACTED]
Date

Lexicon Pharmaceuticals, Inc.
[name]
[name]

[name]
[contact]

MEMORANDUM

To: [REDACTED]

From: [REDACTED], MD

CC: TMF for LX1606.302, [REDACTED]

RE: Race Information for Patient [REDACTED] from [REDACTED] in LX1606.302

Date: November 23, 2015

Dear [REDACTED],

As discussed, please prevent race information for patient [REDACTED], as well as any other subjects from [REDACTED] from being displayed in any tables or listings for any interim or final study report for LX1606.302.

Thank you.

[REDACTED]

[REDACTED], MD
[REDACTED], Clinical Operations
Lexicon Pharmaceuticals

Lexicon Pharmaceuticals, Inc.
[name]
[name]

[name]
[contact]

MEMORANDUM

To: [REDACTED]

From: [REDACTED] MD

CC: TMF for LX1606.302, [REDACTED]

RE: Baseline Data for 302

Date: November 30, 2015

Dear [REDACTED],

As discussed, for any Study LX1606.302 patients missing baseline PPD Laboratory or Frontage (Plasma 5-HIAA) data, please link the Week 48/EOS visit in studies LX1606.301 or LX1606.303 to the Day 1 Visit in Study LX1606.302 in order for us to have complete data set.

Thank you

[REDACTED]
[REDACTED] MD
[REDACTED] Clinical Operations
Lexicon Pharmaceuticals

Note to File

Study Number: LX1606.302

Regarding: Subject Numbers from Phase II Studies

Summary of Situation:

Seven participants completed the LX1606.202 and LX1606.203 Phase II studies and enrolled in the LX1606.302 Phase III extension study. These participants retained their Subject Number from the Phase II study when entering the Phase III study. The table below describes the Subject Numbers and the Investigative site at which they participated in the Phase II and Phase III studies.

Subject Number	Site Name	LX1606.302 Site Number	Investigator Name
[REDACTED]	[REDACTED]	[REDACTED]	[REDACTED]
[REDACTED]	[REDACTED]	[REDACTED]	[REDACTED]
[REDACTED]	[REDACTED]	[REDACTED]	[REDACTED]
[REDACTED]	[REDACTED]	[REDACTED]	[REDACTED]
[REDACTED]	[REDACTED]	[REDACTED]	[REDACTED]
[REDACTED]	[REDACTED]	[REDACTED]	[REDACTED]

[REDACTED]
[REDACTED], Clinical Operations
Lexicon Pharmaceuticals Inc.

[REDACTED]
Date

NOTE TO FILE

To: LX1606-1.301-CS Trial Master File (TMF)
LX1606-1.302-CS Trial Master File (TMF)
LX1606-1.303-CS Trial Master File (TMF)

From: [REDACTED] of Biostatistics and Data Management
[REDACTED] of Biostatistics

Re: Studies LX1606-1.301-CS, LX1606-1.302-CS, and LX1606-1.303-CS (or Studies 301, 302, and 303, for short) – Correcting the Error in the Statistical Analysis Plans (SAPs) Regarding the Scoring Algorithm for the GI.NET21 Scales and Single Items

Date: February 5, 2016

I. **Incident/Finding(s)**

The following incorrect sentence appears in the SAPs for Studies 301, 302, 303:

The scoring algorithm for the GINET 21 scales and single items follows the same rule as the EORC QLQ-C30 **functional** scale scores.

The correct sentence should have been:

The scoring algorithm for the GINET 21 scales and single items follows the same rule as the EORC QLQ-C30 **symptom** scale scores.

Specifically, the correct calculation for each GI.NET21 scale score or single item score is as follows:

$$\text{GI.NET21 Scale or Single Item Score} = \left\{ \frac{RS - 1}{\text{range}} \right\} \times 100,$$

where RS=Raw Score, as defined in the SAPs.

The affected SAPs and sections within the SAPs are: 301 SAP Amendment 1 Final V1.0 (dated 18May2015), Section 8.6.4.2; 302 SAP Final V1.0 (dated 24Nov2014), Section 8.6.1; and 303 SAP Amendment 1 Final V1.0 (dated 24Aug2015), Section 8.6.4.14.

The incorrectly calculated GI.NET21 scores were used in the GI.NET21 tables/listings/figures (TLFs) produced using interim data extractions from the 3 studies. These TLFs were finalized on 13Jan2016 for 301, 22Jan2016 for 302, and 15Jan2016 for 303.

- II. **Action(s) Taken:** Lexicon Biostatistics has made the decision to correct the calculation of the GI.NET21 scores in the ADQS3 analysis dataset and rerun the previously final GINET.21 TLFs using the corrected ADQS3 for each of the 3 studies. The rest of the TLFs, which are not affected by the error, are not to be rerun. The TLFs to be rerun are listed below:

	301	303	302
Tables	14.2.8.1	14.2.15.1	14.2.2
	14.2.8.2	14.2.15.2	
	14.2.8.3.1	14.2.15.3.1	
	14.2.8.3.2	14.2.15.3.2	
Listings	16.2.6.13.7	16.2.6.13.7	16.2.6.1.7
Figures	None	None	14.2.6.2

Lexicon Biostatistics' decision was made subsequent to the finalization of the TLFs, which means after unblinding for 301 and 303. Study 302 was an open-label study. The correction in the calculation of GI.NET21 scores will result in the change in the directionality, but not the magnitudes, of the mean changes in GI.NET21 scores from Baseline within each treatment group and the differences between treatment groups. As such, the previous findings of statistical significance or lack thereof will not change.

[Redacted]
 [Redacted], MS, FRS, [Redacted] of Biostatistics
 and Data Management

[Redacted]
 Date

[Redacted]
 [Redacted], MS, [Redacted] of Biostatistics

[Redacted]
 Date

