7.5 ANALYSIS VISIT WINDOW

In general, all efficacy and safety data will be summarized by study week based on the schedule of events in [Table 1](#). The visits indicated on the eCRF (Baseline Day 1, Week 12, Week 24, Week 36, Week 48, Week 60, Week 72, Week 84/EOS, and 2 Week Follow-up) will be used as the analysis visits for analysis of most safety parameters including vital signs, laboratory examinations, and ECGs.

After mapping the data to the analysis visits as shown, the following rules will apply unless other handling is specified for a particular analysis.

- If multiple records are available within a single analysis visit window, the record closest to the planned assessment day will be selected for analysis.
- If two records are equidistant from the target day, then the later record will be selected.
- If a subject has no record in an analysis window, the subject's data will be considered missing at that time-point.

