9.2 ADVERSE EVENTS

Adverse event is defined as any untoward medical occurrence associated with the use of a drug in humans, whether or not considered drug related. Treatment-emergent AEs are defined as any AEs not present at before first administration of study drug, but occurring after the start of study drug, or if existing before first administration of study drug, increasing in intensity after initiation of study drug. Since this study provides continued access to telotristat etiprate after patients have completed the required study visits in Phase 2 and Phase 3 studies, all AEs reported in this study will be considered TEAEs. Treatment-emergent AEs will be coded by SOC and PT using the MedDRA, version 15.1. All reported TEAEs will be listed, and the verbatim term will be included in the AE listings.

An overall summary of TEAEs will provide, by treatment group and overall, the number and percentage of patients who reported:

- Any TEAE
- Any treatment-related TEAE (definitely related, possibly related, or probably related)
- Any serious TEAE (SAE)
- Any treatment-related SAE
- Any TEAE leading to study drug discontinuation
- Any TEAE leading to study discontinuation
- Any TEAE leading to death

A set of summary tables of TEAEs by SOC and PT will also be presented for the following categories.

- TEAEs
- TEAEs experienced by $\geq 5\%$ of patients in any treatment group
- Severe TEAEs
- Treatment-related and severe TEAEs
- TEAEs leading to study drug discontinuation
- TEAEs leading to study discontinuation
- SAEs
- TEAE of special interests

1003157

Lexicon Pharmaceuticals, Inc.

LX1606.302

Final V1.0

Statistical Analysis Plan

- Treatment-related SAEs
- TEAEs resulting in death

In addition, TEAEs will be summarized separately by the intensity and relationship to study drug. An additional summary of TEAEs will be presented by PT, but not by SOC. This table will be sorted in descending order of overall number of patients reporting PT.

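### The exposure note of 3 November 2015 stops the clock at Week 48 for Study 302 patients without a last dose date, although Study 302 treats to Week 84/EOS

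*SAP*

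**What the plan says.** SAP section 7.2.5 defines treatment duration from the first and last dose dates, and section 9.1 summarises it descriptively by treatment group in the safety population. The note to file of 3 November 2015 amends this for patients still on drug. Its subject is the "Calculation of Extent of Exposure for Open Label Phases of Studies LX1606.301 and LX1606.303, and Study LX1606.302, and in the LX1606 ISS".

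The note gives its reason: "Because many of the patients in the open-label studies are currently continuing treatment, and will not have completed SDAEP forms". SDAEP is the single eCRF page that records first dose, last dose and compliance; it is filled in when a patient completes or leaves early. The note then sets two rules:

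- Where the page holds both dates, exposure runs between them, with no upper limit.
- Where there is no last dose date, exposure is "estimated by using the date of the last recorded visit in the eCRF (scheduled or unscheduled), up to and including the week 48 visit". A bracket adds that Follow-up visits are left out.

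The note says it is meant "for the interim summaries of data which are being provided for inclusion in regulatory submissions".

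For Study 302, SAP section 7.5 lists the visits: "The visits indicated on the eCRF (Baseline Day 1, Week 12, Week 24, Week 36, Week 48, Week 60, Week 72, Week 84/EOS", followed by the 2-week Follow-up. Table 1 shows drug dispensed at Day 1 and at every visit from Week 12 to Week 72.

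**The concern.** One limit is applied to studies of different length. Under SAP section 4.1, Phase 3 patients may enter Study 302 at the Week 48 visit of their parent study, and the memorandum of 30 November 2015 pairs the Week 48/EOS visit of 301 or 303 with Day 1 of 302. So Week 48 is the natural last on-treatment visit for 301 and 303. In Study 302 it lies 36 weeks before the last scheduled treatment visit.

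The error can only go one way. Two patients last seen at Week 72 are treated differently: the one who stopped there and has both dates is credited with 72 weeks, while the one still taking drug is credited with 48. Long-term safety is the primary objective (section 3.1), and duration of exposure is the table that shows how long the patients were on drug. The figures in question go into regulatory submissions.

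**Working it through.** The SAP states no exposure total, so there is no figure to reproduce. The check compares the credited duration with and without the limit.

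**Inputs**
- Duration in weeks = (last dose date − first dose date + 1) / 7 (section 7.2.5). Because study day on or after first dose is event date − first dose date + 1 (section 7.2.3), this equals study day / 7.
- Target days: Week 48 = Day 336, Week 60 = Day 420, Week 72 = Day 504, Week 84 = Day 588 (note to file of 23 November 2015).
- Visit tolerance: ±5 days (Table 1).
- Limit for a patient with no last dose date: the Week 48 visit (note of 3 November 2015).

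**Loss per ongoing patient in Study 302**

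| Last visit | Without limit | As written | Loss | Share lost |
|---|---|---|---|---|
| Week 48 | 336/7 = 48.0 wk | 48.0 wk | 0 | 0% |
| Week 60 | 420/7 = 60.0 wk | 48.0 wk | 12.0 wk | 12/60 = 20.0% |
| Week 72 | 504/7 = 72.0 wk | 48.0 wk | 24.0 wk | 24/72 = 33.3% |
| Week 84, SDAEP page outstanding | 588/7 = 84.0 wk | 48.0 wk | 36.0 wk | 36/84 = 42.9% |

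The visit tolerance moves these little. For Week 72 the loss runs from (499 − 341)/7 = 22.6 to (509 − 331)/7 = 25.4 weeks; for Week 84, from (583 − 341)/7 = 34.6 to (593 − 331)/7 = 37.4 weeks.

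**Effect on the table.** If a share p of the patients summarised is affected, with average loss L weeks, mean exposure is understated by p × L. The documents do not give p. At p = 0 the effect is nil.

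**Could ongoing patients have passed Week 48?** The note of 23 November 2015 refers to an interim extraction of 16 October 2015. Assuming that the exposure summaries use the same extraction, a patient had to enter by about 15 November 2014 to have reached Day 336 (335 days earlier), by about 23 August 2014 to have reached Day 420 (419 days), and by about 31 May 2014 to have reached Day 504 (503 days). Entry dates are not given. The same note says the Week 84/EOS records include "efficacy data assessed at the Week 84 visit for patients who completed the study". This suggests that follow-up had gone past Week 48 for some patients, but it does not show how many were still on drug without a last dose date.

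**Is it corrected later?** No. The note of 23 November 2015 maps efficacy visits only. The memorandum of 30 November 2015 deals with missing baseline laboratory data. The note of 5 February 2016 reruns only the GI.NET21 outputs.

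**The case against.** The best defence is that the intent is visible. The bracket about Follow-up visits reads as an explanation of the limit: stop at the last on-treatment visit. A programmer who knows Study 302 might have used Week 84 without comment. That is plausible, but the written rule names Study 302 and names Week 48, and an addendum to an analysis plan has to be right as written.

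Other parts of the defence stand, and they rule out several stronger readings:

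- A reader might infer that the study's long-term exposure is understated for good. The note is limited to interim summaries. Once SDAEP pages are complete, section 7.2.5 applies unmodified, so a final report need not be affected.
- A reader might infer that Week 84 completers lose 43%. Completers are the patients for whom the SDAEP page falls due. Those with both dates are not limited, so the 36-week loss needs a patient seen at Week 84 whose page is still outstanding. For the same reason it is wrong to say that the rule always strikes the longest-treated patients.
- A reader might infer that adverse event rates are inflated, since events after Week 48 count while the time does not. Section 9.2 plans only counts and percentages: "An overall summary of TEAEs will provide, by treatment group and overall, the number and percentage of patients who reported" each type of event. No planned Study 302 adverse event output divides by exposure. Whether the ISS does so cannot be judged, because its plan is not at hand.
- Whether crude percentages suit a study with unequal follow-up is a separate question of preference. The Week 48 limit does not bear on it.

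**Conclusion.** The limit is wrong for Study 302 as written and should be corrected, although the demonstrated consequence is narrow. It understates the interim duration-of-exposure summary of section 9.1, and the ISS exposure that draws on it, by 12 weeks (20%) for each ongoing patient last seen at Week 60 and by 24 weeks (33%) for each last seen at Week 72. The 36-week (43%) loss arises only with a late SDAEP page. These figures rest on target visit days and on the rule having been programmed literally.

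The total cannot be derived from the document. The note says that many patients across the open-label studies are continuing, but gives no count for Study 302 and none past Week 48; the total is zero if there were none. Adverse event percentages and efficacy results are unaffected. Compliance and amount of drug are unaffected too, because the note makes no such estimate for these patients.

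**What to change.** Amend the second rule of the 3 November 2015 note so that each study has its own limit:

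- Extension periods of 301 and 303: the last recorded visit, no later than Week 48, as now.
- Study 302: the last recorded visit, scheduled or unscheduled, no later than the Week 84/EOS visit, with Follow-up visits excluded.

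Then rerun the interim Study 302 and ISS exposure tables. First check how the exposure variable was programmed. If visits after Week 48 were already used for Study 302, only the note needs correcting so that it matches the outputs. When reporting the rerun, state how many 302 patients had no last dose date and a last visit after Week 48; that number settles the size of the effect.

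The cost is one line in the note and a rerun of a few descriptive tables. No new data and no change to any other analysis are needed.
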